All participants will be instructed to ingest study medications on an empty stomach after an overnight fast, since in all clinical pharmacology studies, LY500307 was administered orally after overnight fast, followed by breakfast approximately 30 minutes after the dosing. The effect of food on LY500307 has not been formally assessed. All participants will receive three capsules of LY500307 or placebo each morning consisting of the following formulations: 1) women randomized to 75 mg LY500307 will receive three capsules each containing 25 mg LY500307; 2) women randomized to 25 mg LY500307 will receive one capsule containing 25 mg LY500307 and two capsules of placebo; and 3) women randomized to placebo will receive three capsules each containing placebo. There will be a 1-1-1 distribution of women in each study arm (i.e., each arm will contain 15 women). A table of random numbers will be used for randomization in this trial. A set of numbers, equivalent to the proposed “N” will be selected and an appropriate block size within that set will be chosen. Within that block, the highest third of the numbers will be assigned to one treatment arm, the middle third will be assigned to the second treatment arm, and the lowest third will be assigned to a third treatment arm. The block size is not revealed to the investigator.

Genetics Studies: Subjects will be invited to provide a 30ml blood sample for genetic characterization studies, including investigation of specific gene polymorphisms (e.g., estrogen, progesterone and androgen receptors) and establishment of lymphoblastoid cell lines (LCLs) and induced pluripotent cell (IPCs) for epigenomic (WES), and transcriptomic (WTS) sequencing. We also plan to perform whole genomic sequencing (WGS) in this protocol in the future. The potential relevance of genetic polymorphisms for women with menstrual cycle-related mood disorders is evidenced in our recent studies (Dubey et. al, 2017; Rudzinskas et. al, 2020), where we have

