During the seven-week study, the effects of LY500307 or placebo on mood symptoms will be monitored with daily symptom rating scales and weekly clinic visits. Outcome measures include the following: Primary outcome measures: self ratings - the Center for Epidemiologic Studies-Depression Scale (CES-D)⁴⁷, observer ratings - the 17-item Hamilton Rating Scale of Depression (HRSD)⁴⁸. Secondary outcome measures: the daily symptom rating form (DRF)⁴⁹ consisting of a 14 item six point likert-type scale measuring the severity of several mood and behavior symptoms including hot flushes (completed on a daily basis at home by each participant); the Beck Depression Inventory (BDI)⁵⁰; a visual analogue scale (VAS) measuring the reported severity of 13 mood and behavioral symptoms (completed at each weekly clinic visit); and whole genome expression/exome sequencing.

During eight weekly clinic visits all women will also have blood pressure, pulse, and weight measured and will be assessed for any side effects to the prescribed medications (including specific evaluations of any complaints of calf pain or other symptoms and signs of blood clots in the legs). In addition, blood samples will be drawn via venipuncture at each of the first seven clinic visits; approximately 50 ml of blood will be collected at each draw (total = 350 ml). This blood will be analyzed for several measures such as the following: estradiol, estrone, FSH, LH, prolactin, testosterone, dihydrotestosterone, SHBG, electrolytes; glucose, CBC, renal, hepatic, thyroid and lipid functions. These measures will be employed to monitor safety parameters of LY500307 (i.e., CBC, renal, hepatic, thyroid and lipid functions), and the potential effects of LY500307 on measures of ER alpha function (see above). Blood samples for estradiol will be processed within 24 hours in the NIH Clinical Center Pathology Service and sent to a staff member not involved with patient

care in order to monitor compliance with estradiol therapy.

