After the completion of this trial, all participants will be evaluated for the presence of clinically significant mood symptoms. Additionally, the results (including symptom ratings and plasma hormone levels) of the study will be reviewed with each participant. If negative mood symptoms or distressing hot flushes are present, we will discuss therapeutic options prior to referral of each participant back to her community health care provider. Additionally, all women will be requested to return for a follow-up clinic visit four weeks after completion of the seven week medication phase (i.e., three week open estradiol treatment, three week double blind placebo/ LY500307 treatment, and one week progestin treatment in non-menstruating women) to evaluate possible adverse effects emerging post-treatment – although no late-onset adverse effects are anticipated. At the time of this follow-up visit an EKG will be performed on all subjects to assess QTc. The options for follow-up in those women who report persisting negative mood symptoms include no treatment with follow-up by community health care provider, initiation of standard antidepressant therapy such as selective serotonin uptake inhibitors with follow-up in community, or resumption of previous menopausal hormone therapy by her community health care provider. Our experience in protocol 03-M-0175, which employed a similar study design with a symptom-provocation paradigm, suggests that in the majority of women depressive symptoms that emerged during estradiol withdrawal were of mild to moderate severity and time-limited. In those women in whom depressive symptoms persisted and were accompanied by distress, either resuming their previous ET or commencing standard antidepressant therapy led to a remission of symptoms. However, in

the fourteen women with past perimenopausal depression who participated in 03-M-0175 and were randomized to estradiol withdrawal, only three women elected to resume ET or use antidepressant therapy because of distressing mood symptoms.

5. Management of Data and Samples

a. Storage

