In this study, we will evaluate at each clinic visit signs and symptoms of any potential adverse events including those associated with deep venous thrombosis, pulmonary embolism, stroke, or severe migraine headaches. Additionally, laboratory tests will monitor renal, hepatic function as well as blood counts and blood lipid levels. Finally, during the last clinic visit an EKG will be repeated to rule out emergent cardiac conduction abnormalities.

2. Estradiol Replacement

Nausea is the most common side effect of estrogen administration. At conventional replacement doses, higher than those employed in this protocol, this complaint seldom interferes with eating, and no weight loss has been reported. Breast engorgement, endometrial hyperplasia and bleeding are also common side effects of estrogen administration. Pre-existing fibroid tumors of the uterus may enlarge under the effects of estrogen; however, at the dosage and for the duration of estrogen administration in this protocol this risk is small.

The relationship between estrogen, both endogenous and exogenous, and the development of endometrial carcinoma has been suggested by several different lines of investigation ⁵¹.

Numerous retrospective case control studies published since 1975 have indicated that postmenopausal exposure to unopposed estrogens for more than one year results in a two to 12 fold increased relative risk for endometrial cancer. A relationship between the dose and duration of estrogen use and the risk for endometrial cancer has also been shown, the risk being increased after one to four years of estrogen use and rising also with the dosage employed. However, the addition of progesterone to estrogen therapy appears to decrease the risk of endometrial hyperplasia and

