b. Conflict of interest: There are no conflicts to report.

c. Role of a commercial company: Eli Lilly will provide suitable amounts of LY500307 to the NIH Pharmacy which will be provided to the contract manufacturing organization (CMO) (i.e., Pine Pharmaceuticals) where quality assurance tests will be performed and appropriately dosed capsules will be formulated. A contract for manufacturing and a quality agreement are being initiated between NIMH and the CMO.

21. Technology Transfer approval from Lilly

In addition to drug substance, Eli Lilly and Company provided the NIH with access to the information in the existing IND (IND - 100,916 for LY500307 study I1A-MC-E001 (ER beta agonist) including information on formulation development and drug product stability. The Clinical Trial Agreement number is 2015-0279. There is no expiration date.

21. Reimbursement and Travel Compensation

Reimbursement of travel and subsistence will be offered consistent with NIH guidelines. Each volunteer will be compensated according to the following schedule:

Screening Procedures:

Initial evaluation, physical exam (2 hours)	30.00
Venipuncture \$20 X 3	60.00
Completion of symptom ratings \$10 X 3	30.00

ER beta trial:

Venipuncture \$20 X 8	160.00
Genetics Bloods	60.00
Clinic visits (weekly) \$20 X 8	160.00
Completion of symptom ratings \$10 X 8	80.00
Transvaginal ultrasound \$100 X 2	200.00

Investigational drugs:

Estradiol Patch \$30 X 2	60.00
LY500307 (or placebo) 21 doses	150.00
Provera	30.00
Total	\$1020.00

Compensation will be prorated for parts completed if subjects do not complete the study. No escort fee will be provided.

Employees and staff who participate during work hours must have permission from their supervisor. NIH employees must either participate outside of work hours or take leave in order to receive compensation.

Flow Sheet

Protocol Schematic

+PMD = Asymptomatic Postmenopausal Women with past perimenopause-related depression

- -Estradiol 100 µg/day (skin patch)
- -Placebo (PO)
- -LY500307 25 mg or 75 mg daily (PO)
- -Provera 5 mg daily (PO)

22. References

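### On the available text, every post-baseline EKG falls about 7 to 35 days after the last LY500307 dose, too late to show a drug-dependent QTc or conduction effect

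*Combined protocol and SAP*

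**What the plan says.** An EKG is part of screening (Section 4.c). After that, two places mention one. Section 7, under Study medications, says "during the last clinic visit an EKG will be repeated to rule out emergent cardiac conduction abnormalities". Section 4.e says "At the time of this follow-up visit an EKG will be performed on all subjects to assess QTc". That visit comes four weeks after the seven-week medication phase, which includes "one week progestin treatment in non-menstruating women". Its purpose is "to evaluate possible adverse effects emerging post-treatment", and the protocol adds that "no late-onset adverse effects are anticipated".

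On dosing, Section 4.a says "All participants will receive three capsules of LY500307 or placebo each morning", and the compensation table in Section 21 lists "LY500307 (or placebo) 21 doses". The double-blind drug therefore covers weeks 4 to 6.

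On the weekly visits, Section 4.d says "During eight weekly clinic visits all women will also have blood pressure, pulse, and weight measured", and adds side-effect checks and, at the first seven visits, blood draws. Sections 8 and 14.b repeat the vital signs, weight and side-effect checks. None of these lists contains an EKG.

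**The concern.** The aim given in Section 7 does not fit the timing. An EKG taken after the drug has left the body can show a lasting or late-appearing change, which suits the post-treatment purpose in Section 4.e. It cannot rule out a conduction abnormality that is present only while the drug is, and it cannot show drug-dependent QTc prolongation. The Section 7 summary of potential adverse effects lists QTc prolongation, and the same section judges earlier QTc findings by whether they depended on dose or concentration.

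Safety of LY500307 is part of the primary objective (Section 2.a). This is the first study of the compound in women, and all earlier human data come from men. Section 10.b has the DSMB review the EKG results; on this schedule it would have no on-drug EKG to look at.

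**Working it through.** **Inputs**
- Phases: 3 weeks open-label estradiol + 3 weeks LY500307 or placebo + 1 week Provera where needed = 7 weeks, which agrees with the stated seven-week phase (Section 4.a).
- Daily dosing, 21 doses, ending with week 6 (Sections 4.a and 21).
- Terminal half-life about 15 hours, in men (Section 1). None is given for women.
- The protocol states no interval from last dose to EKG, so there is no figure of its own to reproduce.

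**Time from last dose to EKG**
- Section 7, if the last clinic visit means weekly visit 8 at the end of week 7: about 7 days.
- Section 4.e, four weeks after week 7: 7 + 28 = 35 days. Section 7 may mean this same visit.
- Section 4.e, if the four weeks run from the last study-drug dose in a woman who needs no Provera: 28 days.

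**Drug remaining**, with half-lives = days × 24 / 15 and share left = 2^(−half-lives)
- 7 days: 168 / 15 = 11.2 half-lives; 2^(−11.2) = 0.0004, or 0.04%.
- 28 days: 672 / 15 = 44.8 half-lives; effectively zero.
- 35 days: 840 / 15 = 56 half-lives; effectively zero.

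The radiolabel study in Section 7 points the same way without using the half-life: about 98% of the radioactivity was recovered within 216 hours (9 days) in six men.

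**If the half-life in women is longer (assumed values)**
- 30 hours: 168 / 30 = 5.6 half-lives, 2.1% left at day 7.
- 45 hours: 168 / 45 = 3.73 half-lives, 7.5% left at day 7 and 0.0002% at day 35.
- For day 7 to match the 24-hour trough share at 15 hours (24 / 15 = 1.6 half-lives, 33%), the half-life would have to be 168 / 1.6 = 105 hours, 7 times the value in men.

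**Dosing-day EKG for comparison**, share of peak left = 2^(−t/15)
- 4 hours after peak: 83%. 8 hours: 69%. 24 hours: 33%.

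All these shares treat the terminal half-life as the whole decline, so they are approximate.

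**Visit calendar** (assumption: visits every 7 days from day 1)
- Visits fall on days 1, 8, 15, 22, 29, 36, 43 and 50. Twenty-one doses from day 22 cover days 22 to 42.
- Visit 7 (day 43) is then about 24 hours after the last dose, unless it is moved to day 42.
- Visit 8 (day 50) is 8 days after the last dose: 192 / 15 = 12.8 half-lives, slightly more than the 11.2 used above.

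**Size of the background risk**
- The hERG IC50 exceeded 2.82 µg/mL. The highest plasma level after 14 daily 100-mg doses was 27.3 ng/mL (both Section 1). The ratio is at least 2820 / 27.3 = 103, at a dose above the trial's 75 mg.

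**The case against.** The strongest case on the other side has four parts.

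- **The absence may be only apparent.** The flow sheet figure is not shown and some pages are missing. The weekly-visit lists are narrative, not a schedule of assessments. Sections 4.e and 7 might also describe two separate EKGs. This limits the point to the available text, but it does not change it: two EKGs would both be off drug.
- **Expected risk is low and oversight exists.** Besides the hERG margin, Section 7 reports no clinically significant EKG changes in the clinical pharmacology studies and only sporadic QTc prolongation in one. Ischemic cardiac disease, renal disease, hepatic dysfunction and significant screening EKG abnormalities exclude a woman, and participants are nearly medication free. Pulse, blood pressure and side effects are checked weekly and electrolytes at seven visits. A medical monitor and a DSMB are in place, and EKG is not an outcome in Section 9. All this stands and keeps the weight modest, although the human EKG evidence is from men only.
- **One EKG per woman shows little.** With no abnormal EKG among 30 women on active drug, the one-sided 95% upper bound on the true rate is 1 − 0.05^(1/30) = 9.5%; for 15 women in one dose arm it is 1 − 0.05^(1/15) = 18%. This also stands. A dosing-day EKG is a modest check, not a definitive QT study. It is still more informative about a drug-dependent effect than one taken at 0.04% of the drug level or less.
- **Moving the EKG gives up the late one.** True, unless both are kept. The loss is small, since Section 4.e expects no late-onset effects. By that visit a woman may also have resumed hormone therapy (Section 4.d) or begun an antidepressant (Section 4.e), which would complicate reading the EKG.

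**Conclusion.** The concern holds. In the available text, no EKG is taken while a woman is on LY500307, and every post-baseline EKG comes at least 11.2 half-lives after the last dose. The schedule can therefore address persistent or late effects but not the on-drug part of the aim in Section 7. The conclusion rests on the 15-hour half-life in men, but it would take a half-life several times longer to weaken it, and then only for the day-7 reading. The consequence is a gap in first-in-women safety information. It is not evidence that participants face a high risk, and it does not touch the efficacy analysis. The change is worth making because it costs almost nothing.

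**What to change.** Take the planned post-baseline EKG at the existing end-of-week-6 visit, where the second ultrasound is due, while dosing continues. Do it on the same day as a morning dose, preferably within a few hours of it. Animal peaks came 0.5 to 8 hours after dosing (Section 1) and no human time to peak is given, so a tighter window cannot be justified from the documents. Add a rule that this visit falls on the day of the last dose, record the dose and EKG times, and name the same visit in Sections 4.e and 7.

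Keeping the follow-up EKG as well is optional. If the present timing is kept instead, add a sentence to Section 7 saying that the EKG addresses only persistent or late post-treatment effects and does not assess QTc or conduction on LY500307.

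The cost is wording in two sections, one visit-day rule and two recorded times per woman. There is no new visit and no added procedure if the EKG is moved; keeping both means one extra EKG per woman. The downside of moving it is losing the late EKG. No dose, treatment or stopping rule changes.

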mg), as this will, in effect, enable us to compare selective ER beta agonism with mixed (ER alpha and beta) agonism, since the higher 75 mg dose could mitigate the recurrence of depressive symptoms by acting through ER alpha. We also will monitor other possible targets of ER alpha activation in these postmenopausal women including plasma luteinizing hormone (LH) levels, plasma prolactin secretion, and endometrial thickness (by vaginal ultrasound). These measures were selected for the following reasons: First, plasma LH levels are increased in postmenopausal women, and studies in mice demonstrate that ER alpha is responsible for ongoing negative feedback effects of estradiol on pituitary LH secretion ³²⁻³⁴; consequently, LY500307-related decreases in plasma LH levels would suggest an ER alpha action. Second, prolactin secretion also has been identified in preclinical studies to be mediated by ER alpha ^{35,36}; consequently, an LY500307-related increase in plasma prolactin secretion would suggest ER alpha activity. Finally, increased endometrial tissue, as measured by vaginal ultrasound, also would suggest the presence of ER alpha activity. These additional outcomes will assist in our efforts to distinguish ER beta activity from ER alpha activity in this protocol.

Medication Administered in this Protocol

Selective Estrogen Receptor beta agonist LY500307: LY500307 is an orally active, selective estrogen receptor beta (ER beta) agonist designed to maximize binding to the ER beta receptor and minimize binding to the estrogen receptor alpha (ER alpha). LY500307 was initially developed for the treatment of benign prostate hyperplasia (BPH). However, due to inadequate efficacy in prostate volume reduction or improvement in International Prostate Symptom Score (IPSS), the benefit-to-risk balance failed to support further development of LY500307 for the BPH indication. LY500307 was selected for use in this protocol since it is the only ER beta selective agonist that both has been

approved by the FDA for use under an IND (held by Lilly) in humans and has evidence to support its ability to penetrate the central nervous system.

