After the three-week baseline period and the determination that ET does not precipitate symptoms, women will be randomized to one of three arms as follows: LY500307 at a dose of 25 mg per day, LY500307 at a dose of 75 mg per day, or matched placebo for three weeks. Once the three weeks of LY500307 or placebo treatment is completed, non-menstruating women will receive one week of Provera (5 mg/day) at the end of the trial to induce a progestin withdrawal bleed. The justification for employing two separate doses of LY500307 is that the lower dose (i.e., 25 mg) may be insufficient to effectively produce agonist effects at ER beta. Prevention of the emergence of estradiol withdrawal-induced mood symptoms at the 75 mg dose (but not the 25 mg dose) would suggest either a dose-dependent agonism at ER beta or the requirement for activation of ER alpha. The latter possibility will be examined by monitoring ER α activity at the levels of the endometrium, the pituitary (plasma LH and prolactin), and possibly hypothalamus (plasma LH³³), which will help us evaluate potential ER alpha actions accompanying the higher dose of LY500307. Of note, the 75 mg daily dose is within the safety margins established by Lilly.

After the trial, those women who were taking ET prior to the study will be re-started on their previous HT regimen unless they request to continue the withdrawal from HT under medical supervision. Outcome measures will include standardized mood and behavioral rating scales. The main comparisons in this study will be between LY500307 and placebo in women with a past history of perimenopause-related depression. Results will be analyzed by analysis of variance for mixed effects and post-hoc Bonferroni testing.

Weekly visits and daily mood ratings:

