ET (three weekly measures) and DB treatment (three weekly measures). Analyses will be performed with SAS Version 9.2 software (SAS Institute, Inc, Cary, NC), using PROC MIXED (for mixed models). For each symptom rating and blood hormone level, the predictor variables of interest, DB treatment (placebo or LY500307), will be modeled as fixed effects. The covariance pattern across time will be structured as first-order autoregressive. We will use the Kenward-Roger method for computing the degrees of freedom for tests of fixed effects.

For each of the symptom outcomes, we will perform analyses to explore the effect of DB medication in the two treatment groups. We will first examine if symptoms changed from baseline (i.e., OL ET [weeks 1-3 of the trial]) to DB treatment phase (i.e., weeks 4-6 of the trial) in any of the three randomization groups (as described above). For the second analysis, if necessary, we will include the mean of the baseline (OL ET) symptom measure (for each symptom) as a covariate and compare differences in symptom ratings across each of the three randomization groups to test for effects of DB treatment. Plasma levels of estradiol, estrone, prolactin, LH and FSH during DB treatment also will be analyzed across randomization groups. For all analyses the value of the estimator (“least square means” in SAS terminology) and associated standard error of the estimator and p values will be reported. The p values will be adjusted for multiple comparisons ($k=3-6$) by the Bonferroni method, and two-sided $P < 0.05$ will be considered statistically significant.

Clinical characteristics (tables 1-3) in women with past PMD will be compared to ensure similarity across groups and include the following measures: age, BMI, menstrual bleeding, weekly average hot-flush severity scores > 2 (minimal severity), CES-D scores > 16 (consistent with clinically significant depressive symptoms of at least moderate severity ^{1;96}), and CES-D scores > 8 and < 16 (consistent with subsyndromal depression ⁹⁷⁻⁹⁹). We will employ Fisher’s exact test for categorical variables and Student’s t-tests for continuous variables.

b. Power analysis

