Based on the results of protocol 03-M-0175 ¹² and with standardized differences of .6 to .7 (and consistent with a prior meta-analysis of estrogen's effects on depressed mood ¹⁰⁰), 10 -15 women will be required in each of the three treatment cells to achieve a power of 80% with an $\alpha = 0.05$ to detect a significant difference between LY500307 and placebo with analyses of variance with repeated measures and Bonferroni t-tests in the principal outcome measures of HRSD and CES-D scales ¹⁰¹. We intend to recruit up to 80 women for this trial through this protocol. Dropouts will be replaced. Since LY500307 has never been administered to women, there is no data available to estimate the sample size needed to evaluate safety measures. Safety measures (unblinded) including symptom inventories, clinical evaluations, laboratory results, and results of EKG of all women participating in this study will be reviewed by the DSMB.

11. Human Subjects Protection

Subject selection:

a. Subject selection will be equitable. All subjects must meet the inclusion and exclusion criteria listed in Section 4. We will select physically healthy adult female individuals. The proportion of ethnic minorities (vs. Caucasians) in the total sample will be approximately consistent with the overall U.S. population proportions. The specified age range for participants in this study (i.e., ages 45 – 65 years) was selected to match the sample selection criteria we previously employed in protocol 03-M-0175. The lower age limit was to avoid enrolling women with early menopause prior to age 45 and the upper age limit would restrict participants to those who had menopause by age 55 (and therefore not women who had menopause after age 55 years). Thus we wish to study women who experienced menopause within the more normal range between ages 45 and 55 years.

b. Justification for exclusion of children:

We will exclude children or minors because the study population is women with past

perimenopausal depression.

c. Justification for exclusion of vulnerable subjects:

Those without consent capacity are excluded because the research question can be answered by enrolling only adults who can provide their own consent and there is no direct benefit for these participants. Therefore, the risks outweigh the benefits for this population.

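### The ER alpha markers are compared without a stated baseline covariate, and some without any stated analysis, so a non-significant marker cannot by itself support absence of ER alpha action

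*Combined protocol and SAP*

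**What the plan says.** **Role of the markers.** Section 1 explains why LH, prolactin and endometrial thickness were chosen and concludes: "These additional outcomes will assist in our efforts to distinguish ER beta activity from ER alpha activity in this protocol". Section 4.d (Double-blinded Randomization phase) says that a benefit at 75 mg but not at 25 mg could reflect either dose-dependent ER beta agonism or a need for ER alpha. It continues: "The latter possibility will be examined by monitoring ER α activity at the levels of the endometrium", and adds the pituitary and possibly the hypothalamus. Section 9.b lists LH, FSH, prolactin, lipids and endometrial thickness as the measures of relative ER alpha and ER beta impact.

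**Analysis.** Section 10.a puts symptom ratings and hormone levels into a mixed model with treatment as a fixed effect and an AR(1) covariance. The mean open-label value enters as a covariate, if necessary, for symptom measures. On hormones the text then says "Plasma levels of estradiol, estrone, prolactin, LH and FSH during DB treatment also will be analyzed across randomization groups". For all analyses, least square means, standard errors and p values are to be reported. On multiplicity it says "The p values will be adjusted for multiple comparisons ($k=3-6$) by the Bonferroni method". The threshold for significance is 0.05, two-sided. Section 10 does not mention endometrial thickness or lipids.

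**Data available.** Section 4.d has blood drawn at each of the first seven weekly visits. It also has one transvaginal scan in week 3 of open-label estradiol and one after three weeks of study drug.

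**The concern.** If mood symptoms are prevented, particularly at 75 mg only, the mechanistic reading depends partly on whether the ER alpha markers moved. Section 1 says what a positive marker would suggest. No section says how to read a marker that shows no significant difference, and none gives an expected shift, an SD, a margin or an interval criterion.

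The stated analysis is also less precise than the data allow. Women differ in LH, prolactin and endometrial thickness before randomization. On the natural reading, Section 10.a leaves that variation in the error term for hormones, although each woman's open-label value has been collected. The Bonferroni step guards against falsely declaring a marker shift. For these markers, missing a real shift matters as well, and a larger k makes that more likely. The informativeness of the ER alpha versus ER beta comparison is at stake; the primary mood analysis is unaffected.

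**Working it through.** **The plan's own figure.** There is none for the markers. The statement in Section 10.b, "10 -15 women will be required in each of the three treatment cells to achieve a power of 80"%, "with standardized differences of .6 to .7", concerns HRSD and CES-D. A plain two-sided two-group calculation at those differences needs 44 or 33 per arm. The stated range can be matched only with repeated-measures assumptions that the plan does not give, so it says nothing about marker power.

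**Inputs from the documents.** 15 women per arm, three arms (Section 4.a), so pooled error df = 45 − 3 = 42. Two-sided alpha 0.05, Bonferroni k = 3 to 6, so per-test alpha is 0.05/3 = 0.0167 to 0.05/6 = 0.0083. Three weekly double-blind values for hormones (Section 10.a); one post-treatment scan.

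**Assumptions.** Marker shift d in between-woman SDs: 0.8 as the working case, with 0.5, 1.0 and 1.5 for range. AR(1) correlation ρ = 0.7. Correlation r between open-label and double-blind values: 0.5, 0.7 and 0.8. None of these values is in the documents.

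**Power on a single value, no covariate.** Noncentrality = d × √(15/2). For d = 0.8 this is 0.8 × 2.739 = 2.19. The critical t on 42 df is 2.018 (no adjustment), 2.494 (k = 3) and 2.769 (k = 6).

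| d (SD) | no adjustment | k = 3 | k = 6 |
|---|---|---|---|
| 0.5 | 27% | 14% | 9% |
| 0.8 | 57% | 39% | 30% |
| 1.0 | 76% | 60% | 50% |
| 1.5 | 98% | 94% | 90% |

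**Power on the mean of three weekly values, no covariate.** Variance factor = [3 + 2(2ρ + ρ²)]/9 = [3 + 2(1.4 + 0.49)]/9 = 0.753. The effective d is 0.8/√0.753 = 0.92 and the noncentrality 2.52. Power is 69% (no adjustment), 52% (k = 3) and 41% (k = 6).

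**Several markers.** On single values, with three independent markers each shifted by 0.8 SD, the chance that all three are non-significant is 0.609³ = 23% (k = 3) to 0.705³ = 35% (k = 6). Positive correlation between markers would raise these figures.

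**95% interval for dose minus placebo, single value.** Half-width = t × √(2/15) × √(1 − r²).
- No covariate, 42 df: 2.018 × 0.365 = 0.74 SD.
- With covariate, 41 df, t = 2.020: r = 0.5 gives 0.737 × 0.866 = 0.64 SD; r = 0.7 gives 0.737 × 0.714 = 0.53 SD; r = 0.8 gives 0.737 × 0.600 = 0.44 SD.
- If the correlation is weak, say r = 0.3, the factor is √0.91 = 0.954 and the half-width 0.70 SD, so little is gained.

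**The case against.** A reader might infer that the sponsor will treat a non-significant marker as proof that ER alpha was silent and so credit ER beta wrongly. The documents do not support that. Section 1 states only what a change would suggest, Section 4.d says the markers will help evaluate potential ER alpha actions, and for a benefit at 75 mg only it keeps both explanations open. What is missing is a rule for reading a null; no wrong rule is stated.

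A reader might also take the single-value figures and conclude that a 0.8 SD shift would be missed 61% to 70% of the time under the plan. For hormones the plan has three weekly values, and the corresponding miss rate is 48% to 59% at ρ = 0.7. The single-value figures fit the scan. Nor need the shift be 0.8 SD: at 1.5 SD power is at least 90% even with k = 6, and several markers are read together.

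Other points stand in part. Baseline adjustment for hormones is not expressly ruled out, since they share the mixed-model sentence with symptoms. Least square means and standard errors are already to be reported, so the plan offers more than significance tests. The markers are secondary, and the 25 mg versus 75 mg contrast also informs the mechanism. Limited power for secondary measures in 45 women is unsurprising.

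These points narrow the concern without removing it. The covariate is written for symptoms only, endometrial thickness and lipids have no stated analysis, and no interval-based reading is specified.

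**Conclusion.** The concern holds in a limited form. As written, Section 10.a does not use open-label marker values that are already collected, and it leaves some markers without an analysis. Under the assumed 0.8 SD shift, one marker would be detected about 41% to 52% of the time from three weekly values, or 30% to 39% from one value, so non-significance alone is weak evidence against ER alpha action. These figures rest on the assumed shift and, for the weekly values, on ρ = 0.7; large shifts would be found reliably.

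The gain from baseline adjustment depends on how well values on estradiol predict values after withdrawal, which the documents do not tell us. The change is worth making before unblinding because it needs no new data.

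**What to change.** In Section 10.a:

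1. State a model for every ER alpha marker, including endometrial thickness and lipids, with the woman's own open-label value as a covariate: the mean of the weekly open-label draws for blood markers, and the pre-randomization scan for endometrial thickness.
2. Report each dose-minus-placebo difference with an unadjusted 95% confidence interval beside the planned Bonferroni-adjusted p value.
3. State that ER alpha involvement will be described from that interval, that is, from the size of shift it does and does not exclude, and not from non-significance.

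**Cost.** A few sentences and model lines, and one degree of freedom per model. No extra visits or samples are needed. A claim of pure ER beta action becomes harder to make.

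**Optional.** Taking the markers out of the Bonferroni adjustment would raise power but allow more chance findings. An equivalence margin could be fixed before unblinding, but with 15 per arm and no covariate, two one-sided 5% tests have 0% power for a 0.5 SD margin and 42% for 0.8 SD when the true difference is zero. Both are judgement calls and not part of the required change.
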